Statistical analysis plan (SAP)

Official study title: Effects of exercise in prostate cancer patients initiating androgen deprivation therapy: A randomised controlled trial

NCT number: Not yet assigned

Date: Version 1.1, 06/12/2018

Sponsor: University of East Anglia, [name]

Prepared by: [name], Postdoctoral researcher in exercise and cancer survivorship, Department of Sport, Exercise and Rehabilitation, Northumbria University, Newcastle upon Tyne, UK

1. Objective

The main objective of this study was to evaluate whether exercise can reduce treatment-related adverse effects in prostate cancer patients initiating androgen deprivation therapy (ADT).

2. Primary outcome

The primary outcome was whole-body fat mass at 3-month endpoint, as measured with Bioelectrical Impedance Analysis and concurrent Bioelectrical Impedance Vector Analysis using a single-frequency, phase-sensitive 50 kHz analyser (BIA-101, RJL/Akern Systems, Firenze, Italy). This method is highly valid for measuring changes in body composition (1). Fat mass was chosen as the primary outcome because adiposity has shown a high propensity to increase during the initial phases of ADT (2), more so than other measures (3), which highlights the importance of targeting body fat at this stage of treatment.

3. Secondary outcomes

The secondary outcomes were as following:

- Feasibility (recruitment rates, attrition, acceptability of the outcome measures, exercise adherence, adverse events)
- Body mass
- Body composition (fat-free mass, skinfold thickness at suprailiac and subscapular sites)
- Anthropometry (waist, hip, mid-upper arm, forearm, mid-thigh and calf circumferences)
- Cardiorespiratory fitness (peak oxygen consumption, ventilatory anaerobic threshold, ventilatory equivalents for oxygen and carbon dioxide at the anaerobic threshold, oxygen pulse, oxygen uptake efficiency slope)
- Hand grip strength

- Biomarkers (total cholesterol, LDL-C, HDL-C, triglycerides, prostate specific antigen, testosterone, sex hormone binding globulin).
- Gleason score
- Risk of cardiovascular disease (QRISK®2-2017)
- Patient reported outcomes (The Functional Assessment of Cancer Therapy-Prostate questionnaire, Functional Assessment of Chronic Illness Therapy-Fatigue questionnaire, Godin Leisure-Time Exercise questionnaire).

4. Sample size

To our knowledge, Cormie et al. (4) is the only previous study to have investigated the effects of exercise in prostate cancer patients initiating ADT on whole-body fat mass, reporting an adjusted MD between experimental and control groups of -1.4 kg ($p = 0.001$) at 3-months. A standard deviation (SD) of 1.6 kg was obtained from the MD and p -value using established guidelines (5). Therefore, 44 participants (22 per group) were required to detect a between-group difference of 1.4 kg assuming $SD = 1.6$ kg, numerator $df = 1$, $\alpha = 0.05$ and $1-\beta = 0.8$, which was calculated using G*Power version 3.1 (6). An attrition rate of 20% was also considered.

5. Statistical analysis

Analyses will be performed by intention to treat using SPSS (IBM SPSS, version 24.0, Chicago, IL). Descriptive statistics (mean \pm SD) will be presented at baseline to characterise participants. Feasibility outcomes will also be presented with descriptive statistics (i.e. recruitment rates, attrition, adherence and adverse events). Between-group differences in outcomes at 3-month and 6-month endpoints will be assessed by analysis of covariance (ANCOVA) with baseline values as covariates. The adjusted mean differences with 95%

confidence intervals (CIs) from the model will be presented. Statistical significance will be set at a two-tailed $p < 0.05$.

6. Missing data

To increase precision of estimates and comply with intention to treat, missing data at 3-month and 6-month endpoints will be multiply imputed using the Markov chain Monte Carlo (MCMC) algorithm with 20 iterations. At the end of the 20 iterations, one imputed data set is created and the process was repeated to generate 20 imputed data sets, which will then be pooled according to Rubin's rules (Rubin, 2004). For participants who have missing data at 3-months, baseline values and other covariates (treatment group, age, Godin score) will be entered into the imputation model. When data are missing at 6-months, baseline and 3-month endpoint values with covariates will be used to impute missing values. Outcomes with missing data at baseline will not be included in the analysis.

References

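### Does the sample size of 44 leave the 20% attrition unaccounted for, so that power falls below 80%?

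*SAP*

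**What the plan says.** Section 2 of the SAP fixes the endpoint: "The primary outcome was whole-body fat mass at 3-month endpoint". Section 4 states that "44 participants (22 per group) were required to detect a between-group difference of 1.4 kg assuming" an SD of 1.6 kg, numerator df of 1, alpha of 0.05 and power of 0.8, calculated in G*Power. It closes with one sentence on losses: "An attrition rate of 20% was also considered". No larger number follows, and no visit is attached to the 20%.

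Section 5 plans ANCOVA with the baseline value as covariate at both 3 and 6 months, with a two-tailed 5% test, and reports adjusted differences with 95% confidence intervals. Section 6 plans multiple imputation of missing endpoint values. For a missing 3-month value, "baseline values and other covariates (treatment group, age, Godin score) will be entered into the imputation model".

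**The concern.** Three figures stand side by side in Section 4: 44 participants, 80% power and 20% attrition. If 44 already delivers 80% power only when nobody is lost, and 44 is also the number randomised, the three cannot all hold. The power claim for the primary outcome would then be too favourable, and the confidence interval wider than planned.

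The missing time point adds to the doubt. A 20% loss by 3 months bears directly on the primary comparison, whereas a 20% loss by 6 months bears on it only in part. Imputation would not be expected to rescue the position. Baseline value and treatment group are already in the ANCOVA, so only age and Godin score bring anything new to a missing 3-month value.

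**Working it through.** **Inputs.** From SAP Section 4: difference 1.4 kg, SD 1.6 kg, numerator df 1, alpha 0.05, power 0.8, two equal groups, attrition 20%. From Section 5: two-tailed test, baseline as the one covariate.

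**1. Reproduce the 44.** The effect size is f = 1.4/(2 × 1.6) = 0.4375. For total N, the noncentrality is λ = f² × N and the error df are N − 3 (two groups, one covariate). Power is the probability that a noncentral F(1, N − 3, λ) exceeds the central 95% point.

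| N with 3-month data | λ = 0.1914 × N | Power |
|---|---|---|
| 43 | 8.23 | 79.9% |
| 44 | 8.42 | 80.9% |

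So 44 is the smallest total that reaches 80%. A two-sample t calculation with 22 per group also gives 80.9%. The SAP's figure is reproduced and contains no allowance for losses.

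**2. Could 44 already include the 20%?** A one-sided t test needs 17 per arm (80.3%), and 17/0.8 = 21.25 rounds up to 22 per arm. That arithmetic also leads to 44, but it contradicts the F test with numerator df 1 in Section 4 and the two-tailed criterion in Section 5. It can be set aside.

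**3. Reading A: 44 is the number analysed.** The number to randomise is 44/(1 − 0.20) = 55, or 56 for equal arms (28 per group). After 20% loss from 55, 55 × 0.8 = 44 remain and power is 80.9%. If the 20% is cumulative to 6 months, at most 20% is lost by 3 months. Power for the primary outcome then lies between 80.9% (44 men) and 89.0% (all 55). Even the cruder inflation 44 × 1.2 = 52.8, taken as 53, leaves 53 × 0.8 = 42.4 and power of 79.4%.

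**4. Reading B: 44 is the number randomised.** With all 20% lost by 3 months, 44 × 0.8 = 35.2, about 35 men, remain. Here λ = 0.1914 × 35 = 6.70 and power is 70.9%.

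- The difference detectable with 80% power rises from 1.38 kg (44 men) to 1.56 kg (35 men).
- The expected 95% CI half-width, t(0.975, N − 3) × 1.6 × √(4/N), rises from 0.97 kg to 1.10 kg.
- The chance of missing a true 1.4 kg difference rises from 100 − 80.9 = 19.1% to 100 − 70.9 = 29.1%.

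Smaller losses by 3 months give power between 70.9% and 80.9%. The SAP gives no figure from which to choose a point in that range.

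**5. Which reading does the text support?** The 44 is presented as what the calculation needs in order to detect 1.4 kg, and that is what a power program returns: participants with data. Attrition comes afterwards, as something taken into account in addition. No sentence in the SAP says that 44 will be randomised or recruited. The wording favours Reading A.

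**The case for a change.** The strongest case for a change is that this section raises attrition itself and then does not finish the sum, so it is not simply a matter left to another document. A reader cannot tell from Section 4 alone whether 44, 20% and 80% are compatible. The two readings differ by about 10 percentage points of power (80.9% against 70.9%). Attrition is also a listed feasibility outcome in Section 3, so a planned figure with a date would give the observed rate something to be compared with. The repair would be one or two sentences.

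Part of this stands. The arithmetic is right, 44 holds no allowance, and the number to randomise and the timing of the 20% are not written in the SAP. It does not follow that a stated figure is wrong. The power loss needs two things that the SAP does not say: that 44 is the randomised total, and that the whole 20% is gone by 3 months. On the more natural reading the three figures agree, and uncertainty about timing can only help the primary comparison.

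**Conclusion.** No change to the plan follows. The sample size calculation is correct as stated, and 44 is the complete-data requirement, with 80.9% power. The wording favours treating 44 as the evaluable number, which implies 55 randomised (56 for equal arms) at 20% loss, and the 80% claim then holds. The fall to about 71%, with 1.56 kg detectable at 80% power, is a conditional worst case on the less likely reading.

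What remains is an unwritten definition: evaluable or randomised, 3 months or 6. A recruitment target commonly stands in the protocol, and a statistician would fill the gap by dividing 44 by 0.8. Writing it down would alter no model, test, estimate or interval; the adjusted difference and its 95% CI will show the precision actually reached.

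This conclusion rests on two assumptions: that the sentence on attrition means an allowance in addition to 44, and that any 20% quoted for 6 months is cumulative. If the protocol were to give 44 as the number randomised, the first would fail and the stated power would be too favourable by up to about 9 points (80 − 71). The validity of the analysis would still be unaffected.

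### Does a single 5% significance rule covering 57 to 59 secondary and 6-month tests leave the plan open to chance claims of benefit?

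*SAP*

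**What the plan says.** Section 2 fixes a single primary endpoint: "The primary outcome was whole-body fat mass at 3-month endpoint". It also explains the choice: adiposity tends to rise early in androgen deprivation, more than other measures do. Section 4 sizes the trial on that endpoint only: "44 participants (22 per group) were required to detect a between-group difference of 1.4 kg". Section 3 lists all other measures under the heading of secondary outcomes.

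Section 5 then gives the analysis: "Between-group differences in outcomes at 3-month and 6-month endpoints will be assessed by analysis of covariance (ANCOVA) with baseline values as covariates". Adjusted mean differences with 95% confidence intervals are to be presented. The decision rule follows: "Statistical significance will be set at a two-tailed $p < 0.05". One group of outcomes is handled differently: "Feasibility outcomes will also be presented with descriptive statistics (i.e. recruitment rates, attrition, adherence and adverse events". The SAP contains no multiplicity adjustment, no testing hierarchy and no statement that secondary or 6-month results are exploratory.

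**The concern.** The word for what is tested in Section 5 is unrestricted, and the 5% rule follows it without any limit to the primary endpoint. Read literally, every non-feasibility measure at both times can be declared significant at 0.05. The list is long and the objective in Section 1 is broad: it speaks of adverse effects of treatment in general, not of fat mass. If fat mass at 3 months showed no difference, a report could pick out a chance result among the many others, call it statistically significant and present it as meeting the objective. With this many tests, some chance results below 0.05 are to be expected.

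**Working it through.** **1. The plan's own figure.** Inputs from Section 4: difference 1.4 kg, SD 1.6 kg, numerator df 1, alpha 0.05, power 0.80. The effect size is f = (1.4 / 1.6) / 2 = 0.4375. With the noncentral F distribution, power is 0.7999 at N = 43 and 0.809 at N = 44. The stated 44 (22 per group) is reproduced. It uses the full 0.05 for one test, which is right for a single primary endpoint.

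**2. Number of other tests.** Counting the non-feasibility items in Section 3:

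| Group | Measures |
|---|---|
| Body mass | 1 |
| Body composition (fat-free mass, two skinfolds) | 3 |
| Circumferences | 6 |
| Cardiorespiratory fitness | 6 |
| Grip strength | 1 |
| Biomarkers | 7 |
| Gleason score | 1 |
| QRISK2 | 1 |
| Questionnaires, one score each | 3 |
| **Total** | **29** |

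Two time points plus fat mass at 6 months give 29 x 2 + 1 = 59 tests. If Gleason score is not measured again at follow-up, it is 28 x 2 + 1 = 57. Questionnaire subscales would raise the count. The Section 6 rule that drops outcomes with missing baseline data could lower it.

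**3. Chance results under a complete null.** The expected number with p < 0.05 is 57 x 0.05 = 2.85 to 59 x 0.05 = 2.95, whatever the correlation between tests. In one direction only it is 57 x 0.025 = 1.425 to 59 x 0.025 = 1.475, if every measure has a favourable direction. The SAP states no directions. Leaving out seven measures whose favourable direction is unclear (Gleason score, Godin score, SHBG, testosterone, and forearm, mid-upper arm and calf circumferences) gives 22 x 2 + 1 = 45 tests and 45 x 0.025 = 1.125, but that list is a matter of judgement.

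The chance of at least one false benefit depends on correlations the SAP does not give. For 57 tests with one assumed common correlation it is 47% at 0.3, 33% at 0.5 and 21% at 0.7. Under independence it is 1 - 0.975^57 = 76%.

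**4. What this does to the trial's conclusion.** The primary test rejects when its own p-value is below 0.05. That event does not depend on any other test, so its error rate is 0.05 whether there are 0 or 59 others. The figures in step 3 would become an error rate for the trial's claim only if success could be declared on any one of the tests. The SAP has no such rule: Section 2 selects one endpoint and Section 4 powers that one.

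**5. What a change would alter.** Suppose the word significant were kept for fat mass at 3 months and the rest were labelled exploratory. The ANCOVA models, the adjusted differences and the 95% intervals would be the same. A 95% interval excludes zero when the p-value from the same model is below 0.05, so as many intervals would exclude zero by chance as before: 2.85 to 2.95 expected under the complete null.

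**The case for a change.** The strongest case for the concern is textual. A rule for significance belongs in an SAP, this SAP states one, and it separates only the feasibility outcomes from it. The ranking in Sections 2 and 3 is not carried into Section 5. The remedy asks for no adjustment, only a sentence or two, and the broad objective makes a selective reading possible.

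The reading of Section 5 and the count stand. So does the observation that a label would help a reader, at almost no cost. The step from there to a fault does not. The ranking does not need repeating in Section 5 to be in force, because calling a measure secondary already says that it does not carry the main conclusion. No sentence says that a secondary or 6-month result would meet the objective; that harm is a guess about a future report. A statement on how secondary results will be read may also sit in the protocol, which was not available for this review. Finally, statisticians differ on the best course here: a label, a fixed hierarchy, a formal adjustment, or unadjusted secondary tests shown with intervals. The SAP's choice is one of these, and it already commits to the adjusted differences and intervals that a reader needs.

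**Conclusion.** The concern does not hold. The count is right: 57 to 59 non-primary tests as worded, with about 2.9 expected below 0.05. That figure assumes exercise affects nothing, fitness included. This is a limiting case for a trial planned on a 1.4 kg difference in fat mass. The smaller directional counts and the probabilities of at least one false benefit rest further on assumed directions and correlations.

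None of this reaches the primary conclusion. One endpoint at one time point is named, justified and powered, and its error rate is 5%. What is left is the absence of an interpretive label, whose addition would change no analysis or result. Secondary and 6-month p-values below 0.05 should be read as unadjusted, as the ranking in Sections 2 and 3 already implies.

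### A missing 3-month value is imputed without the man's observed 6-month value; listing it would be a small, free gain in precision if some men miss month 3 and return

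*SAP*

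**What the plan says.** Section 2 fixes the primary time point: "The primary outcome was whole-body fat mass at 3-month endpoint". Section 5 analyses both visits: "Between-group differences in outcomes at 3-month and 6-month endpoints will be assessed by analysis of covariance (ANCOVA) with baseline values as covariates".

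Section 6 opens with its purpose, "To increase precision of estimates and comply with intention to treat", and says that "missing data at 3-month and 6-month endpoints will be multiply imputed using the Markov chain Monte Carlo (MCMC) algorithm with 20 iterations", giving 20 data sets pooled by Rubin's rules. It then lists predictors for each visit:

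- Month 3, for participants with "missing data at 3-months, baseline values and other covariates (treatment group, age, Godin score) will be entered into the imputation model".
- Month 6: "When data are missing at 6-months, baseline and 3-month endpoint values with covariates will be used to impute missing values".

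The only figure on loss of data is in Section 4: "An attrition rate of 20% was also considered". The SAP does not say how many men are expected to miss month 3 and attend month 6.

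**The concern.** As written, the lists run one way: month 3 informs month 6, but month 6 does not inform month 3. The shorter list applies to the primary endpoint.

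The point concerns only intermittent missingness, that is, a man with no 3-month measurement who is measured at 6 months. His 6-month fat mass is still analysed in the 6-month ANCOVA. It is simply not used to predict his missing 3-month value, although two measurements three months apart on the same man are likely to be correlated beyond what baseline explains. For such men the section serves its own aim of precision less well than it could.

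What is at stake depends on why month 3 is missed:

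- If missingness depends only on the listed predictors, the planned model is valid and only precision is lost.
- If missingness also tracks the 6-month value, adding that value removes the bias to the extent that the men return.
- If missingness depends on the unseen 3-month value itself, adding the 6-month value reduces bias only in part.

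The SAP gives no reason to expect the second or third case, so no size of bias is claimed.

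**Working it through.** **The plan's own figure.** Section 4 gives a difference of 1.4 kg, SD 1.6 kg, numerator df 1, α 0.05 and power 0.80. The effect size is f = 1.4/(2 × 1.6) = 0.4375. The noncentral F test gives power 0.809 at N = 44 and 0.790 at N = 42, so 44 (22 per group) reproduces. Nothing below changes it.

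**Inputs for the gain**

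- f, the share missing at month 3: 20%, taken from the attrition rate in Section 4 (0.2 × 44 = 8.8, about 9 men). Applying it to month 3 is an assumption.
- q, the share of those men who have a 6-month value: not in the SAP; varied from 0 to 1.
- r, the correlation of the 3- and 6-month values after adjustment for baseline and group: not in the SAP; 0.5, 0.7 and 0.9 used.
- Missingness completely at random: assumed.

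**Formula (large sample).** Without the 6-month value, the variance of the 3-month difference is proportional to 1/(1−f). With it, the part of the residual variance that month 6 explains (r²) is estimated from everyone with either value, and the remainder only from men with a 3-month value:

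r²/(1−f+fq) + (1−r²)/(1−f).

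Example with r = 0.7, f = 0.2, q = 0.25: 0.49/0.85 + 0.51/0.80 = 1.2140, against 1/0.80 = 1.25. The ratio is 0.9712, its square root is 0.9855, and the SE falls by 1.45%.

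Fall in SE with 20% missing:

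| Share returning | r = 0.5 | r = 0.7 | r = 0.9 |
|---|---|---|---|
| 0% | 0% | 0% | 0% |
| 10% (about 1 man) | 0.3% | 0.6% | 1.0% |
| 25% (about 2 men) | 0.7% | 1.5% | 2.4% |
| 50% | 1.4% | 2.8% | 4.6% |
| 100% | 2.5% | 5.0% | 8.5% |

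With 10% missing and r = 0.7, the falls are 0.3%, 0.7%, 1.3% and 2.5% at 10%, 25%, 50% and 100% return.

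**Simulation at the planned size.** Settings: N = 44, effect −1.4 kg, residual SD 1.6 kg, r = 0.7, 20% missing completely at random, age and Godin score explaining no residual variance, normal-regression imputation with 20 data sets, and ANCOVA on group and baseline. The planned and joint models were run on the same 6,000 trials. The SE is the empirical SD of the pooled estimates; for the planned model it is 0.5650 kg.

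| Share returning | Joint-model SE (kg) | Fall | Monte Carlo error (points) |
|---|---|---|---|
| 0% | 0.5655 | none | 0.19 |
| 10% | 0.5622 | 0.5% | 0.24 |
| 25% | 0.5555 | 1.7% | 0.31 |
| 50% | 0.5504 | 2.6% | 0.34 |
| 100% | 0.5374 | 4.9% | 0.43 |

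These agree with the formula within Monte Carlo error. Mean estimates were −1.40 to −1.41 kg under both models, so neither shows material bias.

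**In kilograms.** The 95% CI half-width is about 1.96 × 0.565 = 1.1 kg. At r = 0.7 the formula narrows it by about 0.007 kg (10% return), 0.016 kg (25%), 0.03 kg (50%) and 0.06 kg (100%).

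**In power.** If 44 are randomised and 20% are missing, the large-sample SE is 1.6 × √((4/44)/0.8) = 0.539 kg. Power is Φ(1.4/0.539 − 1.96) = 0.738. A quarter returning raises it to 0.744, 0.750 or 0.758 at r = 0.5, 0.7 or 0.9.

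**The case against.** The case for leaving the text alone has several parts.

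**It is not an error.** The planned model contains baseline and treatment group, so it is compatible with the ANCOVA. It shows no bias in simulation and leaves the sample size untouched. This stands, and it is why the point has the lowest priority. It remains a point because Section 6 states its predictor lists explicitly, and a list at least as good is available at no cost.

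**A joint model may already be intended.** One MCMC procedure is named for both endpoints. Its 20 iterations would do little under a strict one-way scheme, since outcomes missing at baseline are excluded and, if the covariates are complete, nothing needs cycling. This is a fair inference, but the lists do not say it. A second analyst following them literally would leave month 6 out.

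**Men lost to attrition seldom return.** This stands: low return is the more natural reading, and the figures for full return are an upper limit that no longer describes attrition at all.

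**The gain cannot be seen in one trial.** Re-imputing fixed simulated data sets (N = 44, 9 missing, 20 imputations) with different seeds moved the reported SE by about 4% (SD) and the estimate by about 0.06 kg. That exceeds the expected SE gain of 0.6–1.5% at 10–25% return. The gain is real on average but would not be noticeable in a single report.

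**The 3-month analysis might not wait for month 6.** The SAP does not state the timing. However, it imputes both endpoints in one procedure, and nothing points to a separate earlier analysis.

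**Enrolment may be larger than 44.** If attrition was allowed for by enrolling 44/0.8 = 55, the absolute SE and kilogram gains shrink by about 10% (√(44/55) = 0.894). The percentage gains do not change.

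**Conclusion.** The point holds as an optional improvement. Read literally, Section 6 leaves the observed 6-month value out of the imputation of the 3-month primary endpoint. The cost is some precision, and only for men who miss month 3 and come back.

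With 20% missing completely at random and a residual correlation between 0.5 and 0.9, the likely gain is 0.3–2.4% of the SE at 10–25% return. It is zero if all losses are permanent and at most 8.5% if every man returns and the correlation is 0.9. The return share and the correlation are assumptions, because the SAP gives neither. The validity of the primary analysis is not in question under the missing-data assumption that the plan relies on.

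**What to change.** State in Section 6 that each outcome has one joint imputation model containing its baseline, 3-month and 6-month values, treatment group, age and Godin score, so that a missing visit is imputed from all observed ones. If that is already the intention, say so and amend the two predictor lists to match. Settle this before the data are analysed, since the choice affects the primary estimate.

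The 20 iterations, 20 data sets, Rubin's rules and the ANCOVA stay as they are. The cost is a wording change and one more variable in the imputation procedure, using a measurement the plan already analyses. It needs no additional participants or assessments.

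### Excluding outcomes with a missing baseline conflicts with the SAP's own intention-to-treat analysis, and the sentence can be read two ways

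*SAP*

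**What the plan says.** Section 5 (Statistical analysis) sets the principle: "Analyses will be performed by intention to treat using SPSS". It also sets the model: differences at 3 and 6 months "will be assessed by analysis of covariance (ANCOVA) with baseline values as covariates".

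Section 6 (Missing data) gives the purpose and scope of imputation: "To increase precision of estimates and comply with intention to treat, missing data at 3-month and 6-month endpoints will be multiply imputed". For a missing 3-month value, "baseline values and other covariates (treatment group, age, Godin score) will be entered into the imputation model"; for a missing 6-month value, the 3-month value is added. The section then closes with "Outcomes with missing data at baseline will not be included in the analysis".

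The SAP does not name a modified intention-to-treat set, give a reason for the exclusion, exempt the primary outcome, or ask for a count of exclusions or a sensitivity analysis.

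**The concern.** ANCOVA needs a baseline value for every man analysed, so the closing sentence decides who is in each analysis. It allows two readings.

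- **Participant level.** The preceding sentences deal with participants who lack a value, so this is the natural reading. A randomised man without a baseline leaves that outcome's analysis even if his endpoint was measured, while a man with a baseline and no endpoint stays. The analysed set then differs from the randomised set and can differ from one outcome to the next.
- **Outcome level.** The grammatical subject is the outcome, so the words can also mean that an outcome with any missing baseline is not analysed at all. What is reported would then depend on the data, and even the primary comparison could be lost. This is less likely to be meant, but nothing rules it out.

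The rule also works against the precision aim in section 6. It discards men whose endpoint was observed, whereas imputing an endpoint from little more than the ANCOVA's own variables adds almost no information on the treatment effect.

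**Working it through.** **Inputs from the SAP.** Section 4: difference 1.4 kg, SD 1.6 kg, alpha 0.05, power 0.8, 44 men (22 per group), and for dropout, "An attrition rate of 20% was also considered". Section 2: "The primary outcome was whole-body fat mass at 3-month endpoint".

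**Assumed inputs, because the SAP gives none.** Within-group baseline-to-endpoint correlation r of 0.5, 0.8 or 0.97. Baselines missing per arm: 2 or 4 of 22 (9% or 18%), and 3 or 5 of 27 (11% or 19%). The 27 per arm comes from 44/0.8 = 55, taken as 54.

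**Step 1: reproduce the planned size.** f = 0.5 × 1.4/1.6 = 0.4375. The noncentrality is f² × N = 0.1914 × 44 = 8.42. With one covariate, the noncentral F on 1 and 41 df gives power 80.9%; at N = 43 it gives 79.9%. The 44 is reproduced.

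**Step 2: cost of exclusion for the primary outcome.** The same formula gives 79.0% at 42 analysed, 77.9% at 41 and 76.9% at 40. Each man lost costs about one percentage point.

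**Step 3: how much of that imputation could recover.** A man with an endpoint but no baseline carries the unadjusted variance 1.6²/(1 − r²) instead of 1.6². Relative to a complete record he is worth 1 − r²: 0.75 at r = 0.5, 0.36 at 0.8 and 0.06 at 0.97. With 4 of 22 missing at r = 0.5, the effective number per arm rises from 18 to 18 + 4 × 0.75 = 21, so variance falls by 1 − 18/21 = 14%. At r = 0.8 it is 1 − 18/19.44 = 7%, and at 0.97 it is 1 − 18/18.24 = 1%. This ignores imputation noise.

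**Step 4: simulation.** 8,000 runs per setting, 20 imputations, Rubin's rules, true difference −1.4 kg, residual SD 1.6 kg, baselines missing completely at random. The entries are SDs of the estimate in kg; variance reduction = 1 − (imputing/excluding)².

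| Per arm | Missing per arm | r | Excluding | Imputing | Variance reduction |
|---|---|---|---|---|---|
| 22 | 2 | 0.5 | 0.509 | 0.494 | 6% |
| 22 | 4 | 0.5 | 0.542 | 0.503 | 14% |
| 22 | 2 | 0.8 | 0.508 | 0.502 | 2% |
| 22 | 4 | 0.8 | 0.533 | 0.516 | 6% |
| 22 | 2 | 0.97 | 0.510 | 0.509 | 0% |
| 22 | 4 | 0.97 | 0.546 | 0.547 | 0% |
| 27 | 3 | 0.5 | 0.464 | 0.443 | 9% |
| 27 | 5 | 0.5 | 0.486 | 0.450 | 14% |
| 27 | 3 | 0.8 | 0.463 | 0.454 | 4% |
| 27 | 5 | 0.8 | 0.487 | 0.469 | 7% |
| 27 | 3 | 0.97 | 0.467 | 0.466 | 0% |
| 27 | 5 | 0.97 | 0.490 | 0.488 | 1% |

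Mean estimates under exclusion ran from −1.387 to −1.412, so there is no bias. Power with 22 per arm and 2 missing per arm, excluding against imputing: 0.748 and 0.781 (r = 0.5), 0.768 and 0.781 (0.8), 0.767 and 0.766 (0.97).

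**Step 5: endpoint imputation for comparison.** Imputing the same share of endpoints from baseline and group raised the variance slightly, by 0.3% to 1.2% across all 12 settings, compared with leaving those men out. Age, Godin score or 3-month values could add some information; that was not modelled.

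**Step 6: simpler ways to keep the men.** At r = 0.97 with 4 of 44 baselines missing, filling in the mean or using a missing indicator gives an SD of 0.763 and power of 0.472 or 0.533, against 0.767 for exclusion. At r = 0.5 they do about as well as multiple imputation (SD 0.495).

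**The case against.** The best defence is that the rule is stated in advance and disclosed. Section 6 limits imputation to the two endpoints, and ANCOVA cannot run without the covariate. If baseline is measured before randomisation, which is usual but not stated in this SAP, then dropping men for a missing baseline does not depend on arm and should not bias the comparison. This stands, and it is why the claim is limited to precision and the departure from the declared population. It does not make the analysed set the randomised set.

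A second objection is that a firm contradiction exists only on the participant-level reading, and that the sentence is merely ambiguous. But on the outcome-level reading randomised men with observed endpoints are left out as well, and more of them, so the conflict holds either way.

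A third is that the size rests on assumed rates and correlations, and that imputation may not help fat mass. This is correct. With few or no missing baselines the effect is negligible. A correlation of 0.97 is itself an assumption; it implies a total SD of 1.6/√(1 − 0.97²) = 6.6 kg, which the SAP does not give. In a separate run of 2,500 simulations at 0.97 with 4 missing per arm, power was 0.708 excluding and 0.692 imputing (Monte Carlo standard error about 0.009): no gain, and perhaps a small loss. Nor do the simulations model age, Godin score, two follow-up times or missing endpoints alongside missing baselines. A man missing both baseline and endpoints adds little under any method.

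**Conclusion.** The concern holds and should be fixed. The closing sentence of section 6 removes randomised men from analyses that section 5 calls intention to treat, and its wording does not say whether a man's record or the whole outcome is dropped.

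The size is modest and conditional. Under the assumed rates, imputing baselines instead of excluding them saves 6% to 14% of the variance at correlation 0.5, 2% to 7% at 0.8 and 1% or less at 0.97. For the primary outcome the case therefore rests on the intention-to-treat label and the ambiguity; the precision gain is for less correlated secondary outcomes. No bias is shown and no stated figure is wrong. Confidence is high on the conflict and the ambiguity; how many men are affected is unknown and may be none.

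**What to change.** Replace the closing sentence of section 6 with:

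> A missing baseline value of an outcome will be imputed in the same MCMC model, with treatment group, age, Godin score and the observed 3- and 6-month values of that outcome as predictors, so that all randomised participants stay in each ANCOVA. An analysis restricted to participants with an observed baseline will be reported as a sensitivity analysis.

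If the sponsor prefers exclusion as the main analysis, the SAP should say that it applies to the participant's record for that outcome and not to the whole outcome, call the set modified intention to treat, report the number excluded by arm and outcome, and make the all-randomised analysis the sensitivity analysis. Mean or missing-indicator imputation should not be used where baseline is strongly prognostic, given the loss of power in step 6.

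The cost is one sentence, one more incomplete variable in the existing imputation command and one sensitivity run, with no new data. For an outcome very highly correlated with its baseline, no gain in power should be expected and a small loss is possible. The choice should be fixed before the data are analysed, so that the reading is not chosen with results in hand.
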